## **9 ADVERSE EVENTS - SAFETY**

The late skin toxicities that potentially occur in these subjects are primarily mild and typically hypopigmentation and telangiectasia. All late skin toxicities at the time of the visit will be documented and graded according to CTCAE current version.

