## 2 PROTOCOL SYNOPSIS

STUDY NAME	A Post-market Multi-Center Retrospective-Prospective Study to Assess Long-term Clinical Outcomes of Non-melanoma Skin Cancer Patients Treated with eBx
PRINCIPAL INVESTIGATOR	[name], FACR
SITES	Up to 5 sites will participate
STUDY DESIGN	
This is a retrospective-prospective post-market, on-label, observational study. Patients who completed eBx treatment <math>\geq</math> 5 years ago since final treatment will be identified and any existing data in the patient's record will be collected in addition to conducting follow-up visits for long-term follow-up. The study will include 2 parts:
 
 
1. Retrospective Chart Review: Collect data from patient records who completed eBx treatment a minimum of five years prior to study onset. The history and demographic data will be retrospectively collected from up to 300 subjects previously treated with eBx for the treatment of NMSC.
 
2. Prospective Follow-up: Patients will either return for a minimum of five-year long-term follow-up visits or telehealth (video) for the investigators to assess the lesion site, document absence/presence of local recurrence and long-term skin toxicities after treatment.
 

SAMPLE SIZE	Up to 300 patients will return for follow-up a minimum of five years post eBx treatment.
STUDY OBJECTIVES	
 
1. To evaluate local recurrence of eBx treated lesions in subjects with a minimum of five-year follow-up.
 
2. Assess long-term skin toxicities.
 

PRIMARY EFFECTIVENESS ENDPOINT	Absence of local recurrence at $\geq$ 5-year follow-up at treatment site(s).
SECONDARY SAFETY ENDPOINT	Occurrence of long-term skin toxicities.
ESTIMATED STUDY PERIOD	Follow-up Visits: Estimated to occur over 6 months.
SPONSOR & FUNDING PARTY	
Xoft, Inc., a Subsidiary of iCAD, Inc.  [name]  [name]

STATISTICAL ANALYSES, STUDY MANAGEMENT, EDC, MEDICAL WRITING	
Eminence Clinical Research, Inc.  [name]  [name]  [name]

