## **6 STUDY PURPOSE**

The purpose of this retrospective-prospective study is to evaluate lesions after treatment for BCC or SCC NMSC in order to gain a better understanding of the durability of the treatment, and risk of late toxicities for this patient population.

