## 7.5 Secondary Safety Endpoint

Occurrence of long-term skin toxicities at the prospective follow-up visit.

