## 8 METHODOLOGY

### 8.1 Identifying the Population

The first phase of this study will be to identify patients who completed treatment with eBx at least five years ago prior to study onset and collect history and demographic data, and eligibility data retrospectively from the patient records and on source worksheets.

This phase will include a review of the site's medical records to determine if the source documentation contains the variables that are needed to determine eligibility, and which will be used in the endpoint analyses.

These variables include:

Patient Age

Pathology report for evidence of:

- o Lesion size (cm) / TNM stage
- o Lesion diagnosis (BCC, SCC)

Last treatment date for each location

Lesion location (e.g. face, extremities, neck, nose, scalp, torso)

Data Collected Prospectively:

Recurrence of cancer at prospective follow-up visit

Recurrence occurred prior to prospective follow-up visit

Long term skin toxicity (graded according to CTCAE v.5)

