**Table 1. Case Report Forms**

Form Name	Retrospective Chart Review	Prospective Follow-up and Data Collection
Demographics and History	X	
Eligibility	X	
Assessment of Local Recurrence		X
Assessment of Late Skin Toxicities		X
Grading of Late Skin Toxicities		X

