### **13.2 Statistical Analyses**

This is a multi-center, retrospective-prospective study comparing non-melanoma skin cancer treatment (basal cell carcinoma and squamous cell carcinoma) using Xoft electronic brachytherapy (eBx) results. The primary endpoint is freedom from recurrence at five-year follow-up or longer. The secondary safety endpoint is late skin toxicities as assessed at the time of the prospective follow-up visit. This study is not powered, as it is for the purpose of reporting the number and percent of subjects who had a recurrence and the number and percent of subjects who showed a late skin toxicity at the follow-up visit. The data will be analyzed and reported by subject and by lesion. The final analysis from the study will be reported as descriptive statistics, both categorical and continuous variables, as appropriate.

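### Late skin toxicity is recorded only as present at one visit five or more years after eBx, which gives a valid visit prevalence but not the risk or occurrence named in the purpose and synopsis

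*Combined protocol and SAP*

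**What the plan says.** The aim is stated broadly in two places. Section 6 gives part of the purpose as the "risk of late toxicities for this patient population". The synopsis gives the secondary safety endpoint as "Occurrence of long-term skin toxicities", with no time limit.

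The operative text is narrower:

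- Section 7.5 defines the endpoint as "Occurrence of long-term skin toxicities at the prospective follow-up visit".
- Section 9 sets the collection rule: "All late skin toxicities at the time of the visit will be documented and graded according to CTCAE current version".
- Section 13.2 says what will be reported: "the number and percent of subjects who showed a late skin toxicity at the follow-up visit".
- Table 1 places "Assessment of Late Skin Toxicities", and the grading form, in the prospective column only. The chart-review column holds Demographics and History, and Eligibility.
- Section 8.1 lists no toxicity variable for the chart review. Under prospective data it has one toxicity item, "Long term skin toxicity (graded according to CTCAE v.5", and no separate item for earlier toxicity. For recurrence, the same list has a second item: "Recurrence occurred prior to prospective follow-up visit".

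There is one visit, at least five years after the last treatment, and participation ends with it (Sections 12.1 and 12.2).

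**The concern.** A toxicity present on one day and a toxicity that ever occurred are different quantities. Section 6 and the synopsis lead a reader to expect the second, whereas the forms and Section 13.2 can deliver only the first. A late skin reaction that began after eBx and had gone by the visit, whether it resolved or was treated, has no field in which to be recorded. Where a toxicity persists, the grade recorded is that of the visit day, not the worst since treatment.

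At stake is how the safety result is described. If the visit percentage is published as the risk or occurrence of late toxicity, any error from this source favours the treatment. The reader could not judge its size, because nothing collected would show it.

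**Working it through.** **Is there a figure to reproduce?** No. Section 13.2 says the study is not powered, 300 subjects is a ceiling, and no toxicity rate is assumed.

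**Could earlier toxicity enter by another route?** The synopsis says, in broad terms, that existing record data will be collected. Section 7.1 narrows this to data the protocol requires. Neither the chart variables in Section 8.1 nor the chart-review forms in Table 1 include toxicity, so no route is provided.

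**Direction.** Among the subjects seen, let p be the proportion who ever had a late skin toxicity after eBx. Let r be the share of those subjects with none left at the visit. Then

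expected proportion at the visit = p × (1 − r).

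Since r lies between 0 and 1, this never exceeds p, and the relative shortfall is r. At r = 0 nothing is lost. At subject level, a person with one resolved and one persisting toxicity still counts, so r refers to subjects with nothing left at any included site.

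**Inputs for an illustration.** The documents give neither p nor r for eBx.

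- p = 3.2% and 5.5% are the complication rates quoted in Section 4 from a retrospective external-radiation series (217 previously untreated patients, and 310 patients overall). Complications there meant grade 4 toxicities. These are borrowed values, used as if they were ever-rates.
- p = 10% is an assumption.
- r = 0, 25%, 50% and 75% are assumptions.
- n = 300 is the ceiling in Section 7.2.

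| Ever-rate p | r = 0 | r = 25% | r = 50% | r = 75% |
|---|---|---|---|---|
| 3.2% | 3.2% | 2.4% | 1.6% | 0.8% |
| 5.5% | 5.5% | 4.1% | 2.75% | 1.4% |
| 10% | 10% | 7.5% | 5.0% | 2.5% |

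For p = 5.5% the expected counts are:

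- r = 0: 300 × 0.055 = 16.5 subjects
- r = 25%: 16.5 × 0.75 = 12.4
- r = 50%: 16.5 × 0.50 = 8.25
- r = 75%: 16.5 × 0.25 = 4.1

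**Set against sampling error.** Suppose an exact (Clopper-Pearson) 95% interval were put around the visit figure with n = 300. The probability that it excludes the true ever-rate would be:

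| Ever-rate p | r = 0 | r = 25% | r = 50% |
|---|---|---|---|
| 5.5% | 0.03 | 0.13 | 0.56 |
| 10% | 0.03 | 0.26 | 0.88 |

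At small r the shortfall is hidden by sampling error. At r = 50% it is not.

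**The case against.** The strongest reply is that the endpoint is defined, and consistently. Sections 7.1, 7.5, 9 and 13.2 all tie toxicity to the prospective visit, and the second part of the synopsis design also places the assessment there. For that quantity this mechanism causes no bias. This stands. A reader might infer that the reported percentage is itself wrong. It is not; the fault lies in calling it risk or unqualified occurrence.

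Second, the contrast with recurrence has a reason. Freedom from recurrence at five years or later cannot be established without knowing about earlier recurrences, whereas a visit-day endpoint needs no history. This also stands: the difference is not in itself an inconsistency. It does show that the plan can already collect an event that preceded the visit.

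Third, the earlier period has been studied. Section 5 describes a completed matched-pair study with toxicities among its endpoints and a median follow-up of three years. The same sites are used (Section 11.1), and patients from prior studies will be called (Section 8.2). This is only a partial answer. Section 8.2 also admits patients from outside those studies, and a median of three years leaves a gap before year five.

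Fourth, the form contents are not shown, and the text does not say how a scarred or repaired site would be graded. Some earlier events may therefore still be counted through what they left behind, which would lower r.

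**Conclusion.** The point holds as a mismatch between the stated aim and the measurement. As a prevalence at the visit, the figure is valid. As an estimate of the risk in Section 6, or of the open-ended occurrence in the synopsis, it can only equal the true value or fall below it, by the relative amount r.

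The size cannot be derived from the documents. Section 9 expects mainly hypopigmentation and telangiectasia but does not say how long they last; if they persist, r is near 0 for them. The illustration for 5.5% (5.5% down to 1.4% as r goes from 0 to 75%) rests on a borrowed rate and assumed values of r. It shows how the shortfall scales and is not an estimate for eBx.

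A reader might go further and infer that the shortfall is greatest for serious toxicities, because these are treated while mild colour change stays. The documents do not support that. Section 4 cites late necrosis and grade 4 toxicity as outcomes in other radiotherapy series, but says nothing about whether such events heal, are treated or persist. Nor is the remark in Section 9 that late toxicities are mostly mild a planned conclusion; it is a background expectation.

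The change is worth making, but its absence does not invalidate the visit result.

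**What to change.** 1. Add to the chart review, and to the late skin toxicity form used at the visit, one item per treated site for late skin toxicity before the visit, parallel to the prior-recurrence item in Section 8.1. Record type, worst grade, date, and whether it resolved or was treated. Include matched-pair study records where the sites hold them. Amend the variable list in Section 8.1 and the chart-review column of Table 1 to match.
2. In Section 13.2, report two figures side by side, per subject and per lesion: toxicity present at the visit, labelled *prevalence at visit*, and any late toxicity since eBx by worst grade, labelled a lower bound.
3. Align the wording of the synopsis endpoint and Section 6 with Sections 7.5 and 13.2. If no new data are collected, this step and the *prevalence at visit* label are the minimum, and they resolve the mismatch of terms.

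The cost is one extra block on existing forms, filled from charts already being opened and a visit already being held. No visit or procedure is added. The drawback is data quality: chart recording of toxicity is uneven, and recall and grading five or more years later are imperfect. That is why the second figure should be labelled a lower bound and should not replace the first.

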## **10 RISKS**

Given the nature of this trial there are no risks related to the eBx treatment in this trial, as the treatment occurred previously, five or more years ago. The only risk is to confidentiality of information. The study sites will maintain confidentiality at all times. No subject identifiers will be published or presented from this study. The sponsor and sponsor representatives shall maintain confidentiality at all times.

## **11 STUDY MANAGEMENT**

### **11.1 Site Requirements and Selections**

Study sites will be those that previously participated in the matched pair study with a retrospective-prospective study design. Sites will be associated with and under the approval of an Institutional Review Board (IRB) [45 CFR 46.10(b)]

Sites selected have expressed an interest in the conduct of a controlled study to collect and report long-term outcomes of eBx for the treatment of non-melanoma skin cancer. Each site will execute a clinical trial agreement with the sponsor. The contract will be executed prior to first subject enrollment at the site.

Case report forms will be used to collect data for the prospective visits. These will also be considered source documentation for data not in the patient medical record.

### **11.3 Investigator Responsibilities**

The following responsibilities are required for investigators participating in this study:

1. Have adequate experience in skin cancer treatment and therapies as documented on the physician's Curriculum Vitae (CV).
2. Be familiar with all regulatory requirements associated with the conduct of a clinical investigation and have the desire and time to comply with the requirements of this study.
3. Have access to an appropriate medical facility, staff, training, and equipment necessary for the conduct of this study.
4. Always observe confidentiality throughout this study.
5. Conduct research under an IRB that oversees the conduct of research studies.
6. Have primary responsibility and oversight of this study for the accuracy, legibility and security of all subject data.
7. Have an adequate patient population to meet study requirements.
8. Follow the protocol procedures and provide the clinical monitor with accurate data in a timely manner.

9. Provide direct access to complete patient medical records for the purposes of conducting source document verification by monitoring, audits, IRB review and regulatory inspections(s) throughout the duration of the study.
10. Provide current (signed and dated) CV to the Sponsor at time of site qualification.
11. Provide current medical license to the Study Management at time of site qualification.
12. Sign and date the Protocol Signature Page to signify agreement to participate in this study and comply with all protocol requirements.
13. Attend the Site Initiation Visit as provided by CRO (web-based presentation or on-site) to ensure understanding of the study requirements, case report forms, and data collection.
14. Identify a study coordinator for this study. Working with and under the authority of the Principal Investigator, the study coordinator assures that all study requirements are fulfilled and is the contact person at the site for all aspects of study administration.
15. Maintain a list of appropriately qualified persons to whom the investigator has delegated significant trial-related duties.

#### **11.4 Sponsor Responsibilities**

Xoft is the manufacturer of the Axxent® eBx System and the Sponsor of this study. Xoft has overall responsibility for the study and shall delegate study management to the CRO:

1. Select qualified Principal Investigators and study sites.
2. Select qualified monitors.
3. Provide the Protocol and any subsequent amendments to the centers.
4. Provide appropriate information and training to Investigators and study staff.
5. Ensure that all variations from the protocol are reviewed with the appropriate investigator(s), where appropriate, are reported to the relevant authorities and IRBs.
6. Ensure uniform data collection and protocol compliance.
7. Provide site initiation training (remote or on-site) that will include review of the protocol, Case Report Form (CRFs), CRF completion guidelines,
8. Retain ownership of all clinical data generated in this study and control the use of the data.
9. Protect patient confidentiality.
10. Collect, store and keep secure the following documents:
  - a. A current, signed, and dated Curriculum Vitae for each site PI
  - b. Current medical license for each site PI
  - c. The IRB opinions and/or approvals, in writing, and relevant correspondence
  - d. IRB approved informed consent form
  - e. Protocol signature page signed by the PI at each site

#### **11.5 Monitor Responsibilities**

Study site monitoring (remote or on-site) will be performed by the CRO. Each site will be monitored on-site or remotely on a regular schedule to ensure that the study is conducted in

compliance with sponsor requirements, the protocol, GCP, and the applicable regulations. The monitor will also ensure that the data reported is consistent with the information found in the subject's medical records (source data verification) and in source documents. Monitoring will include the assessment of the site's overall progress, including but not limited to the site's ability to keep accurate records and to report study-related data to the sponsor in a timely fashion. Monitoring of each site will be performed according to the CRO's Interim Monitoring Visits Standard Operating Procedure (SOP) and the monitoring plan. In order to appropriately monitor the progress of the study, the site will provide the sponsors and/or its designees access to all source documents and other information necessary to ensure investigator compliance with the protocol and applicable rules and regulations, and to assess the progress of this study.

The sponsors designees will maintain contact with the investigator and staff throughout the duration of the study by phone, e-mail, and remote or on-site visits. The monitor will compile and file a monitoring report for each visit. Monitoring will ensure continued protocol compliance, adequate patient enrollment, and accurate data reporting.

The monitor will verify:

1. Informed Consent Forms (ICF)s for on-site visits will be obtained from each subject prior to the participation in this study, and the ICF process is clearly and contemporaneously documented in the medical record.
2. For remote visits, informed consent will be provided verbally by the participant prior to commencing with the prospective data collection at the time of the visit. The signature on the informed consent will be waived for remote visits.
3. The data in the CRF are completed and recorded and provided to the study management team (CRO), in a timely manner.
4. Findings of non-compliance are reviewed with the Investigator(s) and disclosed in a written monitoring report
5. Source Data Verification – Risked based monitoring will be implemented, and source data verification will be performed according to the monitoring plan for the Xoft Study.
6. Site Close-Out: At the time of the site close-out visit, the site monitor will collect all outstanding study documents, ensure that the investigator's files are accurate and complete, review record retention requirements with the investigator, and ensure that all applicable requirements are met for the study.
7. Study Materials: Each Site will receive all the necessary materials needed to initiate and participate in this clinical study. The materials include, but are not limited to:
  - Regulatory Binder and Contents
    1. Protocol
    2. Delegation of Authority Log
    3. Subject Screening Log
    4. Training Log
  - Subject Binder
    1. CRFs
    2. Tab for ICF

## **12 INFORMED CONSENT PROCESS: ON-SITE VISITS AND REMOTE VISITS**

### **12.1 On-site Visits Informed Consent**

Potential study subjects will be called to determine interest in participation in the Xoft follow-up study. Should the person be interested, the patient will be scheduled for a follow-up appointment that is in line with the next clinic visit required by insurance or Medicare. Once the patient arrives at the office, the study will be explained, and the consent will be reviewed and any questions the patient may have will be answered. Should the patient agree to be a participating study subject, the informed consent will be signed and dated by the patient and the person providing informed consent. The subject will receive a copy of the consent and proceed with the visit. The investigator (MD or other healthcare professional) who is qualified to participate as an investigator shall assess the treatment locations and document if there is a local recurrence or late toxicity and grade the late toxicity according to CTCAE criteria. Once this is complete the subject has completed study participation.

### **12.2 Remote Visits Informed Consent**

Potential study subjects who choose to participate remotely by a video conference will be scheduled for a call that meets the regulatory requirements of a visit. The video will start with the delegated site personnel reviewing the elements of the informed consent for this study. Once the consent has been provided verbally, the visit may begin. In this scenario, the waiver of informed consent documentation applies. The study site personnel will document that they provided informed consent and that the patient provided verbal approval and consent to participate, with a written informed consent form being waived for these subjects. All California sites will be required to obtain subject acknowledgement/signature in agreement with the California Bill of Rights. The investigator (MD or healthcare provider) who is qualified to participate as an investigator shall remotely assess the treatment locations and document if there is a local recurrence or late toxicity and grade the late toxicity if applicable. Once this is complete, the subject has completed study participation.

Should there be a situation where the lesion on a remote participant is suspect for a recurrence development, the site will proceed with standard of care.

## **13 STATISTICAL CONSIDERATIONS**

### **13.1 Data Collection**

Data will be collected at the study site on case report form and will be entered into the online database by site and/or ECR personnel. The EDC system for the on-line database will be HIPAA compliant and 21 CFR compliant. The data entry personnel will be

separate from the monitoring personnel. Double data entry will take place to ensure accuracy. The following data collection requirements are listed below:

